## **7.0 Privacy and Confidentiality**

The Principal Investigator ([name]) will be responsible for study monitoring to ensure the safety of participants and the validity and integrity of the data. Data will be collected using standardized forms and will only be identified with the ID of the study participant. The codes that link the name of the participant and the study ID will be kept confidential. Study staff will have weekly contact with the PI for care review conferences and supervision, and the PI will be available in-person for additional monitoring as needed. Should a mental health crisis arise, several steps will be followed according to the safety management plan detailed in the sections 'protection from risk' below (7a) and 'risk management plan' above (6b).

### **7a) Protection from Risks**

Privacy/Confidentiality: In the informed consent form, subjects are told that the information they provide, and all findings will be kept strictly confidential, with access limited to the research staff at the JJPVA, and the possible exception of state or federal regulatory personnel. Diagnostic interviewers will only enter coded identifiers on their notes and forms. The only forms that will contain the subjects' names and identifying information will be the consent forms, which will be stored in a locked file at each site. No identifying information is printed on subject data forms or in individual data files. No one but the project staff has access to the master list linking subjects' names to code numbers, and all information obtained is coded by ID. Identifiable information is kept in locked file drawers. Data from assessments will be stored on a secure VA server with no identifying

information. Results are published as group data without the use of characteristics that would identify individual subjects. We quote information only by number in conference discussions, scientific reports, or publications, in order to maintain anonymity. Additionally, the research team will be using the telehealth platform VA Video Connect to complete study procedures which provides a HIPAA- compliant secure and end-to-end encrypted connection to protect participant privacy.

LC-CR groups may be uncomfortable. This project is evaluating the acceptability, feasibility and initial efficacy of newly developed Long-COVID recovery group treatment. Subjects may find the content uncomfortable and may not want to share details of their clinical condition and symptomatology with others. Group members will not be required to disclose the contents of their Long-COVID recovery plans to others and are never required to share information or speak in sessions. Any specific concerns about the Veteran's reactions will be shared with the individual's psychiatrist and mental health case manager.

Long-COVID follow-up assessments might be stressful. Interviewers will receive training in the importance of study information confidentiality, and in how to manage any participant distress that may be associated with responding to research questions and interviews. We have developed a safety management plan for emergent mental health distress and behavior detected on any of the subsequent follow-up assessments. If there is any indication of mental health distress or suicide risk, co-Is [name] and [name] (VA psychologists with expertise in Veteran suicide risk assessment and management) and PI [name] (VA psychiatrist with expertise in clinical and research Veteran suicide risk assessment and management) will be available to evaluate.

EMA surveys will be delivered using ORD's iteration of Qualtrics. Contact information and surveys responses will be stored on their encrypted server. The primary risk involved is the potential for loss of confidentiality. This risk is not expected to be greater than the risk of loss of confidentiality routinely involved in accessing mental health care via a virtual platform. In order to mitigate privacy risks that are inherent to using mobile phones and websites, we will be implementing several strategies.

- First, all information collected in EMA surveys will be gathered via Qualtrics surveys that are protected using SSL certification to ensure the encryption of all information shared between the study website and potential participants. Accordingly, all responses will be encrypted prior to being uploaded to the study server. We will be using the VA Office of Research Development (ORD)'s instance of the Qualtrics application, which resides in the FedRAMP environment. This has been approved under the Authorized to Operate (ATO) to store "moderate level protected health information and personally identifiable information". This level of security is maintained even when participants complete study surveys on personal devices, such as their own mobile devices.
- Study records will be maintained in a secure location (the R: drive) and destroyed according to VA Federal Records requirements in VHA Record Control Schedule (RCS 10-1), currently at 5 fiscal years following the closure of the study.

Participants who consent to enroll in the EMA portion of the study may find may perceive the protocol to be burdensome and may become frustrated with the frequency or repetition of the daily assessments. Based on past research, we expect this frustration to be low in intensity, as most frustrated participants simply choose not to respond to the survey, which alleviates the frustration. Also, the intensity of the proposed protocol (one 3-minute survey per day for one week at a time; three bursts) is considerably lower than the average ecological momentary assessment study (4 surveys per day for 4 continuous weeks; Jones et al., 2019). The risk of excess burden will be further minimized by reducing the length of surveys to the minimum necessary, designing surveys to accommodate skipped questions, encouraging Veterans to end the assessment as soon

as they sense fatigue, and making the daily assessment portion of the original study optional. If a Veteran expresses frustration with the protocol, we will offer to terminate their participation in the daily assessment protocol with no impact on their enrollment in the clinical trial taking place at JJP VAMC. Finally, we will adjust the protocol's length and/or intensity if Veterans report that either of these is unacceptable.

Veterans enrolled in the EMA protocol may experience some discomfort with questions asked in the questionnaires. The daily assessments will ask Veterans to reflect on and report their current mental health and long COVID symptoms, including levels of hopelessness, loneliness, and ability to function. This process may increase Veterans' awareness or focus on their own symptoms or impairment. Though increased awareness is often desirable in treatment and can result in improvements in mental health outcomes, it is possible that increased awareness may increase distress as well. Veterans will be provided with resources (i.e., Clinic contact info, principal investigator info, and the Veterans Crisis Line) at the end of every survey in the event that they need support. They will be encouraged to reach out to the principal investigator to withdraw from the study if the surveys are upsetting (with no impact to the care they receive at their VA or in the main clinical trial), and JJP VAMC mental health providers (primarily the co-investigators on the JJP VAMC clinical trial, who are clinicians for the proposed participants) will be in contact with the principal investigators at both sites if a Veteran shares that the study is upsetting.

### **7b) Sources of Materials**

Sources of research material for the proposed research include the patient self-report measures and questionnaires involved in the project. Clinical and demographic data are derived from patients' assessment results specifically for research purposes. All relevant data is collected separately for each patient and stored in locked areas to ensure confidentiality.

## **8.0 Communication Plan**

All risks and potential complications are discussed with the subjects during consent signing, and any new information regarding risks will be provided by phone immediately. Patients are monitored closely and should any unanticipated findings arise, the IRB will be notified. Supervision and weekly consultation team meetings will provide a forum for study staff/clinicians to review results of ongoing safety monitoring. During this meeting, any concerning results will be discussed, troubleshooted, and a plan of action will be developed (e.g., decisions about referrals to outside treatment services, termination of subject participation. The PI will work in conjunction with the IRB to evaluate any emerging information and determine if and how the study should be continued.

Chart reviews will be conducted during recruitment of each cohort to ascertain which/if participants have an assigned mental health care provider and safety plan (if they have history of suicidal behavior).

Safety monitoring for adverse events (AEs) will be conducted in real time by the Principal Investigators and the research coordinators. The PI will supervise the research and respond directly to patient problems. In the case of AEs, all of them will be indicated on the source documentation for the specific adverse event report form. The PI will determine the severity of the event, will assign attribution to the event, and will monitor the event until its resolution.

Additionally, the PI [name] (licensed psychiatrist), and co-Is [name] (licensed psychologist) and [name] (licensed psychologist), and therapy facilitator [name] (licensed psychologist)

will be available to evaluate through mental health assessments if at any point a participant is displaying psychological distress and subsequent behavior. They and other research staff will be able to alert the participants' primary mental health provider through CPRS in case additional support is needed.

**Developing an Integrative, Recovery Based, Post-Acute COVID-19 Syndrome (PACS)
Psychotherapeutic Intervention, “PACS Coping and Recovery”**

Funding Agency: Rehabilitation Research and Development Service (RR&D) Small Projects in Rehabilitation Research (SPiRE).

NCT05453201

June 1, 2024

JJPVAMC

PI: [name]

Co-I: [name]

Co-I: [name]

Co-I: [name]

All statistical analyses were conducted using the RStudio (version 4.4.2). Item-level missingness (< 0.5% item-level observations) was handled with participant-mean imputation. Little's (1988) missing completely at random (MCAR) test was not significant ($p > .05$) indicating that the data were missing at random. Paired-sample t-tests were used to examine changes in primary and secondary outcomes from pre- to post-treatment. Paired Wilcoxon tests were used when the Shapiro-Wilk test was significant ($p < .05$). The significance level was set at $p < .05$ for all analyses.

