## 5.2 Recruitment Methods

Long-COVID Patients will be recruited through recruitment from James J. Peters VAMC Long-COVID clinical program and clinician referrals. The Bronx had significantly higher rates of COVID-19 infection than other boroughs in New York City. Thus, recruitment of *up to 36 Veterans* is feasible within the 18-month timeframe.

**Limitations and Future Directions.** One potential issue may be the recruitment of Veterans with Long-COVID. However, a strength of the proposed study is it's involving telehealth, making it more appealing to participants and less prone to no-shows. We will also recruit from our in-house Long-COVID center and multiple existing national Long-COVID programs. While the JJPVAMC is diverse in race and ethnicity, our

study may still have a diversity limitation as it will be conducted in an urban northeast VAMC and may not fully generalize to other areas of the USA. Future studies should extend the findings across other VAMCs. During year 2 we will submit a Merit Award to complete the planned follow up study testing the final manualized version of LC-CR (developed in this SPiRE project) in a multi-site clinical efficacy RCT.

Veteran participants will be offered financial compensation for their participation based on completion levels of the following:

Research Procedure for LC-CR	Participant Compensation
Pre-Treatment Baseline Assessment	\$75
Post-Intervention Assessment (Mod 1)	\$75
Post-Intervention Assessment (Mod 2)	\$75
Post-Intervention Qualitative Interview (Mod 2).	\$75

You will also receive a \$50 bonus upon completion of each therapy module (after the first 8 sessions and after the second 8 sessions).

Participants who consent to enroll in the EMA portion of the research study will be compensated for their participation. The JJPVAMC will be responsible for compensating patients. Participants will be compensated per survey initiated (i.e., at least one question is answered). Participants can receive up to \$135 across all three week-long bursts of daily surveys.

At this time, we anticipate providing a maximum of \$135 per person for participating. Each burst listed below lasts for 7 days. The payment schedule is as follows:

- Burst 1, baseline: \$4 per daily assessment initiated
  - Maximum: \$28 for this burst
- Burst 2, mid-treatment: \$5 per daily assessment initiated
  - Maximum: \$35 for this burst
- Burst 3, end of treatment: \$6 per daily assessment initiated
  - Maximum: \$42 for this burst

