## 5.6 Data Analysis

All data will be de-identified before it is entered into a redcap database at the JJPVA over the intranet.

**5a. Statistical approach.** Descriptive statistics will be calculated, and outcome measures will be compared across the time points using repeated-measures mixed models. Data will be used to examine acceptability and feasibility, and iteratively improve the treatment. Then, we will apply for a RR&D VA Merit to determine efficacy of LC-CR in an RCT.

**5b. LC-CR Fidelity Measure.** Our research team (Drs. [name] and [name]) have experience establishing fidelity of psychosocial interventions. After the first pilot, an adherence scale will be created to assess 1) general LC-CR requirements, 2) session specific requirements, and 3) general group psychotherapy requirements.

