## 5.7 Withdrawal of Subjects

The recruitment process will not be coercive or unduly influencing, as participants enter the research study voluntarily and understand that they have the right to withdraw at any time. Subjects will be told that non-participation in the study will not affect any current treatments they are receiving at VA or elsewhere.

There are no consequences if subjects to withdraw from this study. For subjects that withdraw, our research team will work closely with the suicide prevention team to establish contact, assess reasons for discontinuing treatment and attempt to address concerns. This research team will ask for emergency contact numbers and an emergency contact person that may assist us if you drop from treatment or an emergency occurs.

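### A non-significant Little's test is read as showing data missing at random, which it cannot show, and the SAP does not address Veterans without a post-treatment assessment

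*SAP*

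**What the plan says.** The SAP is a single section written in the past tense. On missing data it makes two statements. The first gives an amount and a method: "Item-level missingness (< 0.5% item-level observations) was handled with participant-mean imputation". The second reports that Little's "missing completely at random (MCAR) test was not significant" and reads this as "indicating that the data were missing at random". It gives no test statistic, degrees of freedom, list of variables or sample size for the test.

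The outcome analysis follows: "Paired-sample t-tests were used to examine changes in primary and secondary outcomes from pre- to post-treatment", with paired Wilcoxon tests where normality is rejected. The SAP gives no number enrolled or analysed, no rule for absent assessments and no sensitivity analysis.

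Protocol section 5.2 sets the size at "up to 36 Veterans". Section 5.5 schedules assessments at baseline, after Module 1 and after Module 2. Section 5.7 tells participants that "they have the right to withdraw at any time" and has the team ask why treatment was stopped. Section 5.6 planned a different analysis, in which "outcome measures will be compared across the time points using repeated-measures mixed models", also without a missing-data rule.

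**The concern.** There are two separate problems.

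- **The inference.** The null hypothesis of Little's test is MCAR, and failing to reject a null does not establish it. The SAP then names a different, weaker condition, MAR. Observed data cannot separate MAR from MNAR, because the difference depends on the values that were not seen. If the phrase is loose wording for MCAR, the inference still fails for the first reason.
- **The scope.** Skipped items on returned questionnaires and whole assessments that never took place are different kinds of missingness. The SAP quantifies only the first. A paired test needs both scores, so a Veteran without a post-treatment score drops out of it. If such Veterans exist and differ in how they changed, the pre-post result describes only those who were assessed.

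At stake is what can be concluded about selective loss. The clause is the only statement in the SAP on the missing-data mechanism, and a reader may lean on it when judging the pre-post changes.

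**Working it through.** **The plan's own figures.** Neither the item-level rate nor the p-value can be reproduced. The documents give no item counts, sample size analysed or test statistic.

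**Check 1: can a rate below 0.5% include an absent assessment?**
Inputs: N at most 36 (protocol 5.2) and three waves (protocol 5.5), or two if only pre and post are counted. Assumption: equal items per wave. The protocol schedules the same nine outcome scales at every wave.

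Share of item observations lost with one absent assessment = 1 / (waves × N).

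- Three waves: 1/(3 × 36) = 1/108 = 0.93%.
- Two waves: 1/(2 × 36) = 1/72 = 1.39%.
- At N = 24: 1/72 = 1.39% and 1/48 = 2.08%. The share rises as N falls.
- N needed to stay below 0.5%: more than 1/(3 × 0.005) = 66.7 for three waves, or 1/(2 × 0.005) = 100 for two.

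The equal-items assumption is not critical. At N = 36 the absent wave would have to hold less than 0.005 × 36 = 18% of a Veteran's items, against 33% or 50% under equal items. So either nobody missed an assessment, which the SAP does not state, or such losses lie outside the figure.

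**Check 2: what could a test at this size detect?**
Assumed split: 22 with a post-treatment assessment and 14 without. It borrows the 60% retention criterion in protocol 5.5 (0.60 × 36 = 21.6). That criterion concerns session attendance, so the split is illustrative only. Alpha is 0.05 as in the SAP, taken as two-sided for the t-test because the SAP does not state sidedness. The groups are assumed to differ at baseline by d SD on one scale.

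- Two-sample t-test, 34 df, noncentrality d × √(22 × 14/36) = d × √8.556. For d = 0.5 this is 1.46, power 0.295. For d = 0.8 it is 2.34, power 0.623.
- Joint chi-square over nine scales, 9 df, one scale differing, common correlation r. Noncentrality = d² × 8.556 × f, with f = (1 + 7r) / [(1 − r)(1 + 8r)].

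| r | f | Power, d = 0.5 | Power, d = 0.8 |
|---|---|---|---|
| 0 | 1.00 | 0.13 | 0.31 |
| 0.5 | 1.80 | 0.22 | 0.56 |
| 0.7 | 2.98 | 0.36 | 0.82 |

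At 0.5 SD a miss is more likely than not in every row. At 0.8 SD the answer depends on the correlation.

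**Check 3: loss that depends on the unseen score.**
Simulation with 8,000 runs per setting. Assumed: n = 36, one pre and one post score, correlation 0.6, true change zero, dropout intercept 20% or 40%, log-odds of dropout 0.5 or 1.0 per SD.

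- Dropout driven by the post score or by the change (MNAR): Little's test was non-significant in 69% to 93% of runs. The mean change among those assessed was off by 0.04 to 0.28 SD, and the paired t-test rejected a true null in 5% to 32%.
- Dropout driven by baseline only (MAR): the mean change among those assessed was still off by 0.04 to 0.14 SD. In this setting, even a true MAR statement would not protect a paired test restricted to those assessed.

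**The case against.** The strongest reply is that this is a wording slip with little behind it. The SAP ties the missing-at-random conclusion to Little's test alone. The item-level rate stands in its own sentence as the amount imputed, and filling so few items by participant mean is of little consequence. The SAP never mentions attrition, so it makes no false claim about it. Rewording the clause changes no estimate. All of this stands, and it limits the point to an invalid inference and an omission.

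Four stronger readings are tempting, and the documents do not support them.

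- A reader might infer that the SAP offers the item-level rate as evidence for MAR, or as the study's overall missing-data rate. It does neither.
- A reader might infer that the SAP presents attrition as negligible. It is silent on attrition.
- A reader might infer that Veterans did stop without being assessed. No document says so. Section 5.7 only provides for withdrawal.
- A reader might infer that a biased effect estimate goes into the later RCT. The protocol says the pilot will inform that trial and try out its scales, not that an effect estimate will be carried forward.

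It is also fair to object that the power figures suppose that Little's test covered absent assessments, when the SAP does not say which variables entered it. If it covered item gaps only, Check 2 does not describe the test that was run, and the test then says nothing about absent assessments. In either case the variables need to be named.

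**Conclusion.** The concern holds in two limited parts. First, the clause is wrong as written. This rests on the logic of the test and needs no assumed number. Second, the item-level rate cannot include even one absent post-treatment assessment at 36 Veterans or fewer (minimum 0.93% over three waves, 1.39% over two, with equal items per wave), so the SAP leaves Veterans without a post score unaddressed while its paired tests exclude them.

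The size of any bias is unknown and may be zero. The power figures (about 30% for a t-test and 13% to 36% for a nine-scale joint test, at 0.5 SD) rest on an assumed 22/14 split, one differing scale and a common correlation of 0 to 0.7. They show that a non-significant result would be weak reassurance under those conditions, not that selective loss took place. The simulation is illustrative in the same way.

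**What to change.** 1. Replace the clause with wording such as: *Little's test did not detect a departure from MCAR; with this sample it cannot exclude selective loss and does not address MNAR.* State which variables entered the test.
2. Report the numbers enrolled, assessed at each wave and included in each paired test, with reasons for loss where these were recorded. The contact in protocol section 5.7 asks why treatment was stopped, which may not explain a missed assessment, so some reasons may be unavailable.
3. Tabulate baseline WHODAS 2.0, PHQ-9 and C19-YRS for Veterans with and without a post-treatment assessment, or state that none was missing.

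The cost is a weaker statement about missing data and one extra descriptive table, drawn from study records and baseline scores the protocol already schedules. No new data collection is needed.
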